Patients will be randomized into either the HES 130/0.4 (HES) or standard care group (human albumin 5%) prior to induction of anesthesia (see Randomization above). The study drug (HES 130/0.4 (Voluven) or human albumin 5%) will be delivered to the operating room in similar

packaging and covered with a shroud to conceal the appearance of the solution (see Blinding and Unblinding above).

Intraoperative Fluid Management

On arrival to the operating room, a large-bore intravenous catheter will be inserted. Routine administration of crystalloid fluids will occur throughout the intraoperative period as a continuous infusion to provide carrier solutions for intravenous drugs, inotropic and vasopressor agents, and continuous flow to maintain patency of intravascular catheters. This routine crystalloid administration will consist of approximately one liter of fluid prior to initiation of cardiopulmonary bypass and one to two liters of crystalloid following cardiopulmonary bypass.

Following separation from cardiopulmonary bypass, the patient will be continuously monitored for acute hypovolemia requiring plasma volume replacement. Plasma volume replacement using 250 mL increments of the blinded study drug (HES 130/0.4 or 5% human albumin in similar containers and covered by a shroud) will be administered when indicated by any of the following clinical conditions (Figure 1): 1) the cardiac output/cardiac index experiences a 20% decrease from baseline; 2) the heart rate increases to 20% above baseline; 3) mean or systolic blood pressure decreases 20% from baseline; 4) a 20% increase in vasopressor requirement occurs; 5) a 20% decrease in cardiac filling pressures (central venous pressure, pulmonary artery diastolic pressures). When these conditions are met, the patient will receive 250 – 500 mL of study solution (HES 130/0.4 or 5% human albumin) as a fluid bolus. These parameters will be assessed on a continuous basis during the intraoperative period and the patient will receive the study solution each time these conditions are met. We anticipate that an average patient will receive approximately 750 – 1000 mL study solution during a routine cardiac surgical procedure.

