The randomized HES and standard therapy groups will be descriptively compared for balance on potentially confounding baseline variables (including duration of cardiopulmonary bypass, use of anti-fibrinolytic therapy, preoperative anticoagulant medications, including clopidogrel). Any baseline variable for which the standardized difference (i.e., observed difference in means or proportions divided by the pooled standard deviation of the outcome) is greater than 0.25 will be considered imbalanced and adjusted for as a covariate in each of the below analyses. We will not use P-values to determine baseline imbalance since the P-value is quite dependent on the sample size, whereas the standardized difference is more independent of sample size and thus a better assessment of balance. [A standardized difference of 0.25 is conservative (should be 0.39) based on the expected 2.5th and 97.5th percentiles of the sampling distribution, i.e., $1.96 \times \sqrt{2/n}$ per group = 50 = 0.39.]³⁰ For all analyses of continuous variables, transformations of the data will be made as appropriate to achieve normality and/or meet other model assumptions. If transformations are not successful, non-parametric analyses analogous to those described below will be employed. For example, we might employ a Wilcoxon rank-sum test to compare the groups on IL-6 at a particular time point if the data are not close to a normal or log-normal distribution.

All primary analyses will be modified intent-to-treat (M-ITT), such that the groups being compared will be all patients who are randomized and who undergo surgery. Analyses of the safety outcomes in Aims 1 and 2 will be noninferiority assessments, and so 1-tailed. All tertiary analyses will be 2-tailed tests for superiority. Conclusions about the effect of HES will be confirmatory for the primary outcome (urinary NGAL) and more exploratory for other outcomes. We will also conduct a “per protocol” analysis for the primary outcome and describe whether these results differ from the modified intent-to-treat results. In the per-protocol analysis we will analyze patients according to the treatment received as oppose to the randomized treatment, and only those patients who complete the entire trial according to the protocol will be included. In case of a discrepancy, the M-ITT results will be primary.

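### M-ITT alone decides the NGAL noninferiority claim, although it keeps any randomized surgical patient who received no study solution; such patients can dilute a harmful effect

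*Combined protocol and SAP*

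**What the plan says.** STATISTICAL METHODS defines the M-ITT comparison so that "the groups being compared will be all patients who are randomized and who undergo surgery". Receipt of study solution is not a condition. A per-protocol analysis is planned for the primary outcome. It groups patients by the fluid they were actually given, not by the arm assigned, and it is restricted to completers: "only those patients who complete the entire trial according to the protocol will be included". Its role is to "describe whether these results differ from the modified intent-to-treat results". The tie-break follows: "In case of a discrepancy, the M-ITT results will be primary". Nowhere must the two analyses agree.

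Under Experimental protocol, patients are randomized before anesthesia is induced. Under Intraoperative Fluid Management, study solution is a post-bypass treatment that "will be administered when indicated by any of the following clinical conditions", namely any one of five 20% changes. The same section says: "We anticipate that an average patient will receive approximately 750 – 1000 mL study solution during a routine cardiac surgical procedure". It does not say what share of patients is expected to receive none.

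The primary test is one-sided at 0.025 and is described as confirmatory.

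**The concern.** The hypothesis concerns giving HES. A patient who receives neither HES nor albumin adds no contrast between the fluids, whichever arm they were assigned to. In a superiority trial such patients make success harder. In a noninferiority trial of safety they work the other way: if HES raises NGAL, they bring the observed ratio closer to 1 and make the claim easier.

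At stake is a confirmatory statement that HES is safe for the kidney, reached while the patients who actually received the fluids would not support it. The tie-break leaves no analysis able to prevent that claim.

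**Working it through.** **Inputs from the documents.** Margin 1.15, ln 1.15 = 0.1398. One-sided alpha 0.025, z = 1.960. CV 25%, so log-scale SD = √ln(1 + 0.25²) = 0.2462. Maximum analysed sample 130, taken as 65 per group (1:1 allocation assumed).

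**Assumptions.** A share f of each arm receives no study solution, and allocation has no effect in those patients. The documents give no value of f; 0 to 20% is shown.

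**The plan's own sample size.** n per group = 2 × (1.960 + 1.2816)² × 0.2462² / 0.1398² = 65.2, so 66. Sample size calculations (Aim 1) states 52 for 90% power. At 52 per group these inputs give 82.5%. The stated 52 would follow from a log SD of about 0.220, for instance through a baseline correlation of about 0.45, but the plan does not say so. I therefore use 65 per group, where fixed-design power is 89.9%. Using 52 per group with SD 0.220 gives nearly the same error rates as below.

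**Dilution, fixed design.** If the true ratio in exposed patients is 1.15, the M-ITT log effect is (1 − f) × ln 1.15. SE = 0.2462 × √(2/65) = 0.0432, and ln 1.15 / SE = 3.236. The chance of claiming noninferiority is Φ(3.236 f − 1.960).

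**Dilution, group-sequential design.** I simulated 1,000,000 trials with the Table 3 p-value boundaries and both stopping rules followed. The first safety boundary, printed only as below 0.001, was set at 0.0003.

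| f | M-ITT ratio | Fixed design | Table 3 boundaries |
|---|---|---|---|
| 0% | 1.150 | Φ(−1.960) = 2.5% | 2.0% |
| 5% | 1.142 | Φ(−1.798) = 3.6% | 2.9% |
| 10% | 1.134 | Φ(−1.636) = 5.1% | 4.0% |
| 20% | 1.118 | Φ(−1.313) = 9.5% | 7.5% |

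**Sensitivity to variability.** The quartiles quoted for patients who did not progress (13.5 and 82.9) give a log SD of (ln 82.9 − ln 13.5) / (2 × 0.6745) = 1.345. Then ln 1.15 / SE = 0.592, and fixed-design error is about 2.9% at 10% unexposed and 3.3% at 20%.

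**Cost of a second test.** With no true difference, power in exposed patients alone is Φ(3.236 × √(1 − f) − 1.960): about 88% at 5%, 86–87% at 10% (rounding to 58 per group gives the lower figure) and 82% at 20%. The two test statistics have correlation √(1 − f). Requiring both therefore costs about one point more: bivariate normal probabilities of 87.4%, 85.5% and 81.2%.

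**The case against.** **The unexposed share may be close to zero.** The triggers are broad and assessed continuously, surgical blood loss is also to be replaced, and the expected average is 750–1000 mL. This stands. A reader might infer that M-ITT certainly contains unexposed patients and that the decision is biased. The documents do not support that: they make zero exposure possible but do not show that it happens to a material extent. An average, however, does not rule it out, and the plan neither bounds the share nor commits to reporting it.

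**M-ITT answers a legitimate question.** For the policy of giving HES or albumin when triggered, compared as randomized, the error stays at its nominal level. This also stands. The inflation concerns the effect in patients who received fluid, which is what a statement about the safety of administering HES will be taken to mean.

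**The planned per-protocol analysis is no cure.** A reader might infer that it would expose the dilution and should overrule M-ITT. The documents do not support this either. Someone who met no trigger and received nothing has followed the protocol, so may remain in the per-protocol set. That set is also as-treated and limited to completers, so it gives up randomization, may lose the sickest patients, and can be biased in either direction.

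**A discrepancy would not be hidden.** The plan promises to describe differences and to emphasise estimates and confidence intervals. That helps a careful reader but leaves the formal claim intact.

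**Conclusion.** The point holds conditionally. It is certain that M-ITT alone decides the claim, that it retains any unexposed surgical patient, and that under a harmful HES effect such patients favour noninferiority. The size is not certain. It rests on an assumed unexposed share, the planned 25% CV, equal shares in both arms and no effect of allocation in unexposed patients. Under those assumptions, 5% to 20% unexposed raises one-sided error to between 3.6% and 9.5% in a fixed design, or between 2.9% and 7.5% with the Table 3 boundaries. Near 0% unexposed, or with NGAL variability like that in the quoted quartiles, the effect is small.

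Dilution should not be read as hiding any degree of harm. A true ratio of 1.20 with 20% unexposed becomes 1.20^0.8 = 1.16, still above the margin, and the fixed-design chance of a false claim is about 1.8%. The weakness lies at true ratios close to 1.15.

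**What to change.** Replace the tie-break in STATISTICAL METHODS. Claim noninferiority on urinary NGAL only if it is shown both in M-ITT and in randomized patients who had surgery and received any study solution, analysed in the arm to which they were randomized. If the two disagree, report noninferiority as not established. Report the number and share of unexposed patients by arm.

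Clinicians giving the solution are blinded (Blinding and unblinding), so whether a patient receives any should not depend on arm; the by-arm report checks this. Because both tests must succeed, no alpha adjustment is needed. The plan already uses this all-must-pass logic within the outcome sets of Secondary Aim 2. State whether the rule also applies to a safety claim at the Table 3 interim looks.

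Keep the as-treated completer analysis as supportive only, and state whether a patient who met no trigger belongs to it.

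The cost is SAP wording and one further analysis; volume of study solution per patient is the only extra variable needed. For a fixed design with 90% power, power in the exposed set is about 88% at 5% unexposed, 86–87% at 10% and 82% at 20%, and about one point lower for the joint requirement. If almost everyone is exposed, almost nothing is lost.

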“Following surgery within one hour of arrival to ICU”: These laboratory measurements will be measured within one hour (+/- 1 hr) following ICU arrival (after completion of surgery). The Cleveland Clinic standard of care mandates that patients are transferred immediately from the operating room to an intensive care unit upon completion of surgery for reasons of patient safety. The transition from operating room to intensive care unit occurs promptly and smoothly upon completion of surgery. If a delay occurs for any reason, postoperative laboratory measurements (urine NGAL, urine IL-18) will occur within one hour of scheduled (not actual) departure from operating room. This will ensure that postoperative laboratory measurements are collected at the time when peak values are expected, and a delay in transfer of the patient to the ICU will not impact these laboratory results.

“24 hours (± 2 hours) following surgery”: These laboratory measurement will be occur at 24 hours (± 2 hours) following completion of surgery defined as time of departure from the operating room following surgery or within two hours prior to removal of central venous/arterial lines and urinary catheter if patient is discharged from the ICU in less than 24 hours.

Justification of laboratory measures of kidney function

NGAL (urine) is an early predictor biomarker of acute kidney injury. Postoperative urine NGAL levels correlated with the severity and duration of AKI, length of stay, requirement for RRT, and mortality in cardiac surgical patients.²⁸ A postoperative urine NGAL concentration, using a cutoff value of 100 ng/ml, demonstrated excellent sensitivity and specificity. The postoperative urine NGAL levels correlated with severity and duration of acute kidney injury, length of stay, dialysis requirement, and death.

IL-18 (urine) is a biomarker of acute kidney injury that improved risk stratification and identified patients at high risk for progression of acute kidney injury and worse patient outcomes in cardiac surgical patients.²⁹

Justification of laboratory measures of the inflammatory response.

IL-6 increases during cardiopulmonary bypass and continues to increase in the first few hours after surgery. Increased IL-6 levels correlate with adverse postoperative outcomes.

TNF-α is an early inflammatory cytokine that initiates the inflammatory response and is pyrogenic. TNF-α facilitates leukocyte–endothelial interaction, and elevation of **TNF-α** and has been

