Type I error. The significance level will be 0.025 for the 1-tailed noninferiority tests for the primary outcome and for each set of the secondary outcomes, and 0.05 for each of the 2-tailed superiority tests for tertiary outcomes (i.e., no adjustment for multiple testing for tertiary outcomes).

Our primary hypothesis is that HES 130/0.4 is noninferior to standard care effects on **mean urinary NGAL** measured within one hour of arrival to ICU and 24 following completion of surgery. We a priori define the noninferiority delta for urinary NGAL as a ratio of geometric means (since NGAL data are expected to be lognormal) of 1.15, for an effective delta of 15% of the control group mean. [Note: for this and other outcomes, if the data are non-normal, a log-transformation will be attempted and the treatment effect (if normal on the log-scale) will be summarized as the ratio of geometric means, equivalent to the difference in means of the log-transformed data.] As noted below under “Continuous outcomes measured over time (Primary and Secondary Aims)”, we will assess the treatment effect for the primary outcome in the context of a linear mixed model which allows us to simultaneously assess the effect across the collapsed time points if there is no group-time interaction, or else at specific times if there is an interaction detected. We will conduct tests for noninferiority using treatment effect estimates from the linear mixed model and applying 1-tailed t-tests for noninferiority as described in Mascha and Sessler (2011) [Mascha EJ, Sessler DI: Statistical grand rounds: Equivalence and noninferiority testing for regression models and repeated measures designs. Anesth Analg 2011; 112: 678–87], and with t-statistic as follows:

$$T_{NI} = \frac{\hat{\beta}_1 + \delta}{SE_{\hat{\beta}_1}}, \text{ where } \hat{\beta}_1 \text{ is the estimated treatment effect with standard error}$$

$SE_{\hat{\beta}_1}$ and noninferiority delta of δ .

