In Secondary Aim 1 – **kidney function** – we will assess noninferiority of HES to albumin on each of urinary concentration of II-18 and acute kidney injury as classified by RIFLE criteria, using statistical methods reported below under continuous (urinary concentration of II-18) and ordinal (RIFLE criteria) outcomes. These will be 1-tailed tests for noninferiority, using a noninferiority delta of 15% of the mean (or a ratio of geometric means of 1.15, if data are found to be log-normally distributed) for urinary concentration of II-18 and a noninferiority delta of 1.15 for the odds ratio assessing the effect of HES 130/0.04 on the ordinal RIFLE outcome. The noninferiority delta of 1.15 corresponds to a 15% higher odds of having a worse RIFLE score with HES 130/0.04 versus standard, and is roughly analogous to the 15% difference utilized for the continuous outcomes (urinary NGAL and II-18). A Bonferroni correction will be made to preserve alpha at 0.025 for this aim.

In Secondary Aim 2, the safety outcomes of **coagulation and platelet function** each comprise a set of several variables. Noninferiority of HES to albumin will be assessed for each outcome at the 0.025 level using a noninferiority delta of 15% of the mean (as explained above). We will claim noninferiority of HES to standard within a set if noninferiority is shown on all of the variables in a set. Therefore, no adjustment for multiple testing within a set will be done (i.e., intersection-union test).

Safety conclusions will be based on descriptive statistics as well as statistical tests. Multivariate analyses considering a vector or set of related outcomes may also be performed.

For tertiary aims all comparisons will be 2-tailed tests for superiority and analyses will follow the methods outlined below based on type of outcome variable. Each test will be conducted at the 0.05 significance level since these are exploratory analyses.

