Continuous outcomes measured over time (Primary and secondary aims). For the primary outcome (urinary NGAL) and each of the secondary continuous outcomes which are measured over time (e.g., at baseline, within one hour of arrival to ICU following surgery, and 24 hours following completion of surgery), we will assess the treatment effect of HES 130/0.4 versus standard care using linear mixed effects models (with patient as random effect), adjusting for the baseline value of the outcome and any baseline variables for which balance among the randomized groups was not achieved through randomization. We will adjust for the baseline value of the outcome for efficiency, i.e., to obtain a smaller standard error for the estimate of treatment effect to the extent that the baseline value is correlated with the later time points, regardless of baseline balance. An unstructured within-subject correlation structure will be employed, estimating a distinct correlation parameter for each pair of post-baseline measurement times.

If the treatment group-by-time interaction is significant ($P < 0.15$), the treatment effect for a particular outcome will be assessed at each of the post-baseline time points measured, using a Bonferroni (or other appropriate) correction for multiple comparisons procedure if comparing groups at specific time points. Similarly, correction to the significance criterion will be made in all analyses below when comparing multiple times, as appropriate.

Ordinal outcome. Groups will be compared on the ordinal outcome of the RIFLE criteria (Secondary Aim 1) using proportional odds logistic regression, adjusting for baseline imbalance

as needed. We will assess noninferiority using the approach described above for the primary outcome, where $\hat{\beta}_1$ is the estimated treatment effect in the form of a log-odds ratio.

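### The printed noninferiority statistic has the wrong sign for the plan's own definitions: it tests a ratio of 0.87, not 1.15, and coding, sign of delta and rejection tail are not stated

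*Combined protocol and SAP*

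**What the plan says.** All of this is in Statistical Methods unless noted.

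- **Test statistic** (Type I error and primary hypothesis): "T_{NI} = \frac{\hat{\beta}_1 + \delta}{SE_{\hat{\beta}_1", with β1 the estimated treatment effect, SE its standard error and δ the noninferiority delta. The test is one-tailed at 0.025. No null hypothesis in symbols, treatment coding, sign for δ or rejection tail accompanies it.
- **Margin, NGAL** (same section): "noninferiority delta for urinary NGAL as a ratio of geometric means (since NGAL data are expected to be lognormal) of 1.15", with the effect taken as a difference in log means.
- **Direction of the contrast** (Continuous outcomes measured over time): "we will assess the treatment effect of HES 130/0.4 versus standard care using linear mixed effects models".
- **Direction of harm, NGAL** (Justification of laboratory measures of kidney function): "postoperative urine NGAL levels correlated with severity and duration of acute kidney injury, length of stay, dialysis requirement, and death".
- **RIFLE** (Secondary Aim 1): an odds ratio margin of 1.15, which "corresponds to a 15% higher odds of having a worse RIFLE score with HES 130/0.04 versus standard". The Ordinal outcome paragraph adds "We will assess noninferiority using the approach described above for the primary outcome", with β1 as the log odds ratio.
- **IL-18** (Secondary Aim 1): 15% of the mean, or a ratio of 1.15 if log-normal. For the aim as a whole, "A Bonferroni correction will be made to preserve alpha at 0.025 for this aim".
- **Coagulation and platelet function** (Secondary Aim 2): "Noninferiority of HES to albumin will be assessed for each outcome at the 0.025 level using a noninferiority delta of 15% of the mean".
- **Interim monitoring**: six looks at NGAL, with P-values compared with the safety and non-safety boundaries of Table 3. The Executive Committee section says the interim analysis is programmed beforehand.

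**The concern.** On these definitions harm is β1 > 0, and noninferiority means showing that β1 lies below +ln 1.15. Adding δ to β1 moves the boundary to the other side of zero.

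The consequence depends on the tail, which is not given. With upper-tail rejection, a safety claim becomes more likely as HES raises NGAL, and the non-safety boundary, which was made aggressive so that harm shows early, does not respond to harm. With lower-tail rejection, HES would have to be shown better than albumin by more than 13%.

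This is the decision rule for the only outcome the plan calls confirmatory, and it produces the P-values used at every look. RIFLE shows the conflict most clearly, because there the direction is spelled out and the same statistic is then applied.

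Secondary Aim 2 adds a related gap. A rise in PT or aPTT counts as evidence of coagulopathy (Executive Committee report elements), while for platelet count the low values are the concern (transfusion section). For the thromboelastography variables and aggregation the report elements say only that they worsen. One signed formula cannot serve both directions.

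**Working it through.** **Inputs.** Margin 1.15, so δ = ln 1.15 = 0.1398. CV 25% (Sample size calculations), so the log-scale SD is s = √ln(1 + 0.25²) = 0.246. As a second case, the quartiles 13.5 and 82.9 in the same section give s = ln(82.9/13.5)/(2 × 0.6745) = 1.345. Looks at N = 22, 43, 65, 86, 108 and 130, half per arm. From Table 3, safety is claimed at P ≤ 0.0004, 0.001, 0.002, 0.005, 0.010, 0.021 (look 1 prints <0.001; the alpha spent, 0.0004, is used). Non-safety is declared at P > 0.746, 0.471, 0.256, 0.125, 0.056, 0.021.

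**Boundary.** Setting (β1 + δ)/SE = 0 gives β1 = −0.1398, a ratio of 1/1.15 = 0.870. Setting (β1 − δ)/SE = 0 gives a ratio of 1.15. If IL-18 is analysed untransformed, the printed form's boundary is 0.85 of the control mean.

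**Reproducing Table 3.** With P = Φ((β1 − δ)/SE) and a true ratio of 1.15, simulation gives non-safety crossing probabilities of 0.254, 0.302, 0.218, 0.121, 0.060, 0.025. Table 3 prints 0.254, 0.303, 0.217, 0.122, 0.060, 0.025. This confirms that the boundaries were read correctly. It does not settle the sign, because the printed upper-tail form gives the same values at a ratio of 0.87 by symmetry.

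**Group sequential results** (1,000,000 trials per case, normal approximation, no group-by-time interaction):

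| Log-SD | True ratio | Corrected form | Printed form, upper tail | Printed form, lower tail |
|---|---|---|---|---|
| 0.246 | 1.00 | safety claim about 83% | about 83% | about 0%; non-safety by look 2 in 98% |
| 0.246 | 1.15 | claim 2.0% | claim 99.9% | – |
| 0.246 | 1.50 | non-safety at look 1 in 97% | claim 100%; at look 1 in 97% | – |
| 1.345 | 1.15 | claim 2.0% | claim 18% | – |
| 1.345 | 1.50 | claim 0.1% | claim 55% | – |

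**Hand check of look 1 at ratio 1.5.** SE = 2 × 0.2462/√22 = 0.105.
- Printed form: (0.4055 + 0.1398)/0.105 = 5.19. The critical value for 0.0004 is 3.35, and Φ(5.19 − 3.35) = 0.97 for safety.
- Corrected form: (0.4055 − 0.1398)/0.105 = 2.53. The non-safety cut at P = 0.746 is z = 0.66, and Φ(2.53 − 0.66) = 0.97 for non-safety.

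**Single look, 65 per arm.** SE = 0.2462 × √(2/65) = 0.0432 and δ/SE = 3.236.
- Corrected: claim 2.5% at 1.15; Φ(3.236 − 1.96) = 90% at 1.0.
- Printed, upper tail, at 1.15: Φ(2 × 3.236 − 1.96) > 99.99%.
- Printed, lower tail, at 1.0: Φ(−1.96 − 3.236) = 1e-7.

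At a true ratio of 1.0 the corrected and upper-tail forms agree, so a power check under no effect would not reveal the error.

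**The case against.** The strongest reply is that this is an ambiguity rather than a contradiction. The printed formula is right if β1 is coded albumin minus HES and rejection is in the upper tail, or if δ is entered as −ln 1.15 with lower-tail rejection. The plan describes the contrast in words, not as a model indicator, and it cites a methods paper that may supply the missing conventions. The intent is also plain from the text, confidence intervals are to be emphasised in reporting, and a statistician sits on the Executive Committee. An interval for the ratio read against 1.15 would expose a reversed test.

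Much of this is fair. It shows that the error can be recovered from and is not proof that the analysis will be run wrongly. It does not make the printed rule agree with the plan's definitions. Both rescuing conventions depart from the plan's wording, neither is stated, and for RIFLE the direction is explicit. A programmer preparing the interim analysis would reasonably code the formula as printed.

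Three technical limits stand. The plan specifies t-tests; with 20 degrees of freedom at look 1, the 97% safety crossing at ratio 1.5 falls to about 86%. The standard error used is for one unadjusted measurement, whereas the model pools two postoperative times and adjusts for baseline. The 0.87 boundary applies to log-scale and log-odds analyses, not to untransformed IL-18. None of these changes which side of 1 the boundary falls on.

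**Conclusion.** The concern holds. Taken with the plan's own effect definition, margin and direction of harm, the printed statistic puts the null boundary at 0.87 instead of 1.15 for NGAL, RIFLE and log-transformed IL-18. Followed as written, it gives either a safety claim in 99.9% of trials at the margin of harm (upper tail) or almost no chance of a claim when HES is equivalent (lower tail). The corrected rule gives 2.0% and about 83% in those two situations. The sizes rest on CV 25%, Table 3's boundaries, the normal approximation and no interaction. With the larger spread implied by the quoted quartiles the contrast is smaller but still serious (18% against 2.0% at 1.15). This must be corrected because it is the decision rule for the confirmatory outcome. The missing Secondary Aim 2 directions are a lesser, related gap.

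**What to change.** 1. State β1 = HES minus albumin (log ratio or log odds ratio where applicable) and write the null as β1 ≥ δ.
2. Where higher is worse (NGAL, IL-18, PT, aPTT, and RIFLE coded so that higher is worse), use T = (β1 − δ)/SE with lower-tail rejection, or equivalently an upper confidence limit below the margin. Set δ = ln 1.15 on the log or log-odds scale, or 15% of the mean on the original scale.
3. Tie the level to the plan: Table 3's boundaries for NGAL (0.021 at the final look), the Bonferroni level for IL-18 and RIFLE (0.025/2 = 0.0125 each if split equally), and 0.025 for each Secondary Aim 2 variable. Add the plan's further correction if the interaction path is taken.
4. Where lower is worse, keep T = (β1 + δ)/SE with upper-tail rejection. If such data are log-transformed, say whether the margin is 0.85 or 1/1.15 = 0.87.
5. Add a table of the adverse direction of every Secondary Aim 2 variable: PT, aPTT, R, K, angle, MA, LY30, platelet count and each aggregation test. Noninferiority must be shown on every variable in a set, so one wrong sign can change the conclusion for the whole set.
6. Check that the pre-programmed interim code matches, testing it at a harmful ratio as well as at 1.0.

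The cost is one formula, a sentence on coding and tail, a short table and a code check. Sample size and trial conduct are unaffected.

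### With at most 130 patients, the RIFLE noninferiority test at an odds-ratio margin of 1.15 has at most 3.7% power if the fluids are equivalent, yet it takes half of Secondary Aim 1's alpha from IL-18

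*Combined protocol and SAP*

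**What the plan says.** All references are to the Statistical Methods section of the combined protocol and SAP.

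- **Outcomes.** The Secondary Aim 1 paragraph states: "we will assess noninferiority of HES to albumin on each of urinary concentration of II-18 and acute kidney injury as classified by RIFLE criteria". It adds: "These will be 1-tailed tests for noninferiority".
- **Margin.** For RIFLE the plan uses "a noninferiority delta of 1.15 for the odds ratio assessing the effect" of HES on the ordinal class. The only reason given is that this is "roughly analogous to the 15% difference utilized for the continuous outcomes".
- **Alpha.** "A Bonferroni correction will be made to preserve alpha at 0.025 for this aim". This agrees with the Type I error paragraph: "The significance level will be 0.025 for the 1-tailed noninferiority tests for the primary outcome and for each set of the secondary outcomes". The level per test is not printed; an equal split over two outcomes gives 0.0125.
- **Model.** The Ordinal outcome paragraph specifies proportional-odds logistic regression, with the noninferiority test made on the log-odds ratio.
- **Size.** Sample size calculations (Aim 1) rests on NGAL alone. The maximum analysed is 130. No power is given for RIFLE or IL-18, and no kidney-injury rate is stated.

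**The concern.** A 15% margin on a continuous marker with a small assumed variance can be tested with about 130 patients. A 15% margin on an odds ratio for a four-level clinical outcome asks for far more information. If the trial cannot supply it, the formal result for its clinical kidney outcome is close to fixed before the first patient is enrolled. That outcome bears directly on the trial's rationale, which is kidney injury with HES. A reader could take the failed test as a sign of harm or as a finding, when it would be neither. The alpha set aside for RIFLE is also taken from IL-18, the other outcome in the aim.

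**Working it through.** **Inputs from the plan.** Margin 1.15, so ln 1.15 = 0.1398. One-sided alpha 0.025 / 2 = 0.0125, so z = 2.2414. N = 130; equal allocation is inferred from the plan's 52 per group and 104 in total.

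**Assumptions.** True odds ratio 1, the usual planning value for noninferiority and consistent with the plan's hypothesis of no worsening. Unadjusted model. RIFLE distributions are illustrative, written as % none/Risk/Injury/Failure; Loss and End-stage need weeks to months of follow-up.

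**The plan's own figure.** There is none for RIFLE. The only power-based figure is 52 per group for NGAL. A simple two-group comparison with log-scale SD = sqrt(ln(1 + 0.25²)) = 0.2462 gives 66 per group for 90% power, so the 52 was not reproduced. That is a separate matter, and nothing below depends on it.

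**Power of the RIFLE test.** For a proportional-odds model with 1:1 allocation, the information on the log-odds ratio is I = (N/12) × (1 − Σp³), where p are the pooled category proportions. It cannot exceed N/12. SE = 1/√I and power = Φ(0.1398/SE − z).

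Best possible case:

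- SE ≥ √(12/130) = 0.304
- Power at 0.0125: Φ(0.460 − 2.2414) = Φ(−1.781) = 3.7%
- Power at 0.025: Φ(0.460 − 1.960) = Φ(−1.500) = 6.7%

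The largest observed odds ratio that passes is exp(0.1398 − 2.2414 × SE):

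| Distribution | SE | Power at 0.0125 | Observed OR needed |
|---|---|---|---|
| Upper bound, any distribution | 0.304 | 3.7% | 0.58 |
| Four equal classes | 0.314 | 3.6% | 0.57 |
| 70/18/8/4 | 0.377 | 3.1% | 0.49 |
| 80/12/5/3 | 0.436 | 2.7% | 0.43 |
| 90/6/3/1 | 0.584 | 2.3% | 0.31 |

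Simulating the fitted proportional-odds test (65 per arm, 2,500 runs each) gave 3.6% for four equal classes, 2.8% for 70/18/8/4 and 2.0% for 85/10/4/1.

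**What a failed test would mean.** It fails at least 96.3% of the time (100 − 3.7) when the fluids are equal, and by design 98.75% of the time when the true odds ratio sits at the margin. The result barely separates the two.

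**Sample size needed.** At 90% power, N ≥ 12 × (2.2414 + 1.2816)² / 0.1398² ≈ 7,625, or about 3,800 per arm. With 70/18/8/4 the total is 11,720; with 80/12/5/3 it is 15,685. Conversely, 80% power with 130 patients needs a margin of at least exp((2.2414 + 0.8416) × 0.304) ≈ 2.55.

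**The stated analogy, without reference to sample size.** On the plan's assumed CV of 25%, the NGAL margin is 0.1398 / 0.2462 = 0.57 SD of log NGAL. A proportional-odds model can be read as a latent logistic variable with SD π/√3 = 1.814, so the RIFLE margin is 0.1398 / 1.814 = 0.08 SD. The shared figure of 15% does not make the two margins comparable.

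**Cost to IL-18.** The plan gives no IL-18 variance, so this is only an illustration: a test with 90% power at 0.025 has Φ(1.960 + 1.2816 − 2.2414) = Φ(1.000) = 84% at 0.0125.

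**The case against.** - **The plan already softens this.** It makes only NGAL confirmatory, bases safety conclusions on descriptive statistics as well as tests, and says that estimates and confidence intervals will be emphasised for all analyses. This stands and limits the consequence. But a margin, a test and an alpha split are still specified, and the statement that the study is not powered names binary outcomes, not ordinal RIFLE.
- **A margin expresses tolerable harm, and a strict one cannot falsely reassure.** This stands too. The criticism is not that 1.15 is clinically too tight. It is that the trial cannot test it and that the reason given for it does not hold.
- **The test is not impossible to pass.** Correct. A reader might infer that it cannot succeed, but the 3.7% ceiling is conditional on a true odds ratio of 1. Across the distributions from four equal classes to 90/6/3/1, power is about 7% to 25% at a true odds ratio of 0.7, and 16% to 66% at 0.5. The plan's hypothesis, however, is no worsening, not marked protection.
- **Secondary Aim 2 does not split alpha.** A reader might infer an inconsistency from "Therefore, no adjustment for multiple testing within a set will be done". There is none. Aim 2 claims noninferiority only if every variable in a set shows it, which properly needs no adjustment. Aim 1 allows a claim on either outcome, and there Bonferroni is valid.
- **Dropping Bonferroni would be enough.** It would not: the RIFLE ceiling at 0.025 is 6.7%. Requiring both outcomes to pass would let RIFLE sink the whole aim.

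**Conclusion.** The concern holds. At N = 130, one-sided 0.0125 and a true odds ratio of 1, power is at most 3.7%, and this bound needs no assumption about the rate or spread of kidney injury. The observed odds ratios of 0.43 to 0.49 do rest on assumed any-grade rates of 20% to 30%. Early stopping at an interim look would lower power further. The 0.0125 assumes an equal split over two tests; separate tests of creatinine-based and urine-output-based RIFLE would lower it.

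The loss for IL-18 is certain in alpha (0.025 to 0.0125) but unknown in power. The primary NGAL conclusion is not affected, and the documents do not support reading this point as a flaw in it. It is worth correcting because the change is cheap and the plan otherwise commits to a nearly predetermined formal result.

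**What to change.** In the Secondary Aim 1 paragraph:

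1. Take RIFLE out of the alpha-sharing family. Report its proportional-odds odds ratio with a 95% confidence interval.
2. State that the trial cannot establish noninferiority on RIFLE at 1.15. For scale, with an observed odds ratio of 1 the upper 95% limit would be at least exp(1.96 × 0.304) = 1.81, and about 2.09 with 70/18/8/4 or 2.35 with 80/12/5/3.
3. Test IL-18 alone at one-sided 0.025.
4. Delete the sentence that justifies the odds-ratio margin by analogy with the continuous outcomes.

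The cost is SAP wording, with no added patients or data. The formal RIFLE verdict is given up, and the aim's only formal claim then rests on a biomarker. The trial report should say so, so that an IL-18 result is not read as clinical evidence of kidney safety.
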